#### **4.2. End of Study Definition**

A participant is considered to have completed the study if he or she has completed all phases of the study including the last visit (Visit 5) or the last scheduled procedure shown in the SoA.

The end of the study is defined as completion of the last visit or procedure shown in the SoA in the trial globally.

## 5. Study Population

Prospective approval of protocol deviations to recruitment and enrollment criteria, also known as protocol waivers or exemptions, is not permitted.

### 5.1. Inclusion Criteria

Participants are eligible to be included in the study only if all of the following criteria apply:

1. willing to participate and sign informed consent;
2. ability to read and understand informed consent and study procedures, including able to use the electronic Daily Headache Diary;
3. in good general health based on investigator's judgment;
4. must be between 18 to 65 years of age, inclusive, at time of Visit 2;
5. have migraine with and/or without aura meeting the diagnostic criteria listed in the International Classification of Headache Disorders 3rd edition (ICHD-III; Appendix 5);
6. verification of headache frequency through prospectively collected baseline information during the 28-day screening/baseline phase reporting 4-22 migraine days and no more than 22 total headache days;
7. onset of migraine before age 50;
8. able to differentiate migraine from other primary headache types allowed in the study (e.g., tension-type headache);
9. stable history of migraine at least 3 months prior to screening with at least some discreet headache free periods;
10. not currently taking a migraine preventive OR has been taking a stable dose of a preventive for at least 90 days prior to screening and agrees to not start, stop, or change medication and/or dosage during the study period;  
\* \* participants on migraine preventive should have stable headache pattern
11. women may be included only if they have a negative pregnancy test at screening and baseline, are sterile, or postmenopausal. Women of childbearing potential (WOCBP) engaging in potentially procreative intercourse must use highly effective birth control methods for the duration of the study (i.e., starting at screening). Definitions of WOCBP, sterile and postmenopausal women, male contraception, and highly effective and acceptable birth control methods are to be determined based on investigator's judgment;

12. demonstrated compliance with the electronic Daily Headache Diary during the 28-day screening/baseline phase as defined by entry of headache data on a minimum of 23 days;
13. is willing to wear activity/sleep tracker throughout the duration of the trial;
14. has a smartphone and willing to install activity tracker app on phone.

## 5.2. Exclusion Criteria

Participants are excluded from the study if any of the following criteria apply:

1. unable to understand the study requirements, the informed consent, or complete headache records as required per protocol;
2. pregnant, actively trying to become pregnant, or breast-feeding;
3. history of substance abuse and/or dependence that would interfere study conduction, in the opinion of the Investigator;
4. history of impaired renal function that, in the investigator's opinion, contraindicates participation in this study;
5. suffers from a serious illness, or an unstable medical condition, one that could require hospitalization, increase the risk of adverse events, or compromise data integrity (ie, likely require changes in con meds or lead to other medical investigations or treatments during the study).
6. a psychiatric condition, in the opinion of the investigator, that may affect the interpretation of efficacy and safety data or contraindicates the participant's participation in the study;
7. received nerve blocks or trigger point injections in the previous 8 weeks or plans to receive them during the study;
8. prior exposure in the last 6 months, or 5 half-lives, to biologics or drugs specifically targeting the calcitonin gene-related peptide (CGRP) pathway;
9. has failed more than 3 classes of medications for the prevention of migraine or >6 migraine preventive medications of any type due to lack of efficacy;
10. received any investigational agents within 30 days prior to Visit 1 (6 months for any investigational biological products unless previous study blind has been broken and subject was known to have received placebo);
11. plans to participate in another clinical study at any time during this study;
12. history of medication overuse of opioids or butalbital, as defined by opioid or butalbital use  $\geq 10$  days/month in each of the previous 3 months or during run-in period; Medication

Overuse Headache (MOH) with other medication types will be allowed but must be documented;

13. unstable medication use for migraine prevention (changes in the last 3 months);
14. clinically relevant lab results at screening as determined by the investigator;
15. clinically relevant or significant ECG abnormalities as determined by the investigator, including ECG with QT interval corrected for heart rate (QTc) using Fridericia's correction formula (QTcF) > 500 msec;
16. history of any of the following cardiovascular conditions:
  - a. Moderate to severe congestive heart failure (New York Heart Association class III or IV);
  - b. Recent (within past 6 months) cerebrovascular accident, myocardial infarction, coronary stenting;
  - c. Uncontrolled hypertension as defined by a confirmed systolic blood pressure > 160 mmHg or diastolic blood pressure > 100 mmHg.
17. Subjects known to have active HIV or untreated Hepatitis C infection;
18. score of > 0 on question 9 on Patient Health Questionnaire (PHQ-9) at any visit;
19. have any other condition, that in the judgment of the investigator, would make the participant unsuitable for inclusion, or would interfere with the participant participating in or completing the study.

### **5.3. Screen Failures**

Screen failures are defined as participants who consent to participate in the clinical study but are not subsequently assigned to study intervention at Visit 2. A minimal set of screen failure information is required to ensure transparent reporting of screen failure participants to meet the Consolidated Standards of Reporting Trials (CONSORT) publishing requirements and to respond to queries from regulatory authorities. Minimal information includes demography, screen failure details, eligibility criteria, and any serious adverse event (SAE).

Individuals who do not meet the criteria for participation in this study (screen failure) may be permitted in certain situations to rescreen, after discussion with the study medical monitor. However, participants that test positive, through urine testing, as pregnant, or are determined to be of significant suicide risk, are not allowed to be rescreened.

Rescreened participants should be assigned a new participant number (i.e., different than the initial screening participant number).

## 6. Study Intervention

### 6.1. Study Intervention(s) Administered

#### Description:

Fremanezumab-vfrm is a calcitonin gene-related peptide (CGRP) antagonist subcutaneous injection indicated for the preventive treatment of migraine in adults, see product insert for detailed information.

#### Dosing and administration:

225 mg/1.5 mL solution via single-dose prefilled syringe administered subcutaneously once monthly in the abdomen, thigh, or upper arm.

### 6.2. Preparation/Handling/Storage/Accountability

1. The investigator or appropriately trained and delegated designee must confirm appropriate temperature conditions have been maintained during transit for all study intervention received and any discrepancies are reported and resolved before use of the study intervention.
2. Only participants enrolled in the study may receive study intervention and only authorized site staff may supply or administer study intervention. All study intervention must be stored in a secure, environmentally controlled, and monitored (manual or automated) area in accordance with the labeled storage conditions with access limited to the investigator and authorized site staff.
3. The investigator, institution, or the head of the medical institution (where applicable) is responsible for investigational product accountability, reconciliation, and record maintenance (i.e., receipt, reconciliation, and final disposition records).
4. Further guidance and information for the storage and final disposition of unused investigational product are provided in the Package Insert.
5. See the Package Insert for complete preparation, handling, storage, and accountability details.

### 6.3. Measures to Minimize Bias: Randomization and Blinding

This is an open-label study with one arm; potential randomization and/or blinding concerns are not applicable.

## **6.4. Study Intervention Compliance**

All participants will be dosed at the site and will receive study intervention directly from the investigator or designee, under medical supervision. The date and time of each dose administered in the clinic will be recorded in the source documents and recorded in the Case report form (CRF).

## **6.5. Concomitant Therapy**

Any medication or vaccine (including over-the-counter or prescription medicines, vitamins, and/or herbal supplements) that the participant is receiving at the time of enrollment or receives during the study must be recorded along with:

- Reason for use
- Dates of administration including start and end dates
- Dosage information including dose and frequency

The Medical Monitor should be contacted if there are any questions regarding concomitant or prior therapy.

Participants should not currently be taking a migraine preventive or have been taking a stable dose of a preventive for at least 90 days prior to screening and agrees to not start, stop, or change medication and/or dosage during the study period.

### **6.5.1. Prohibited Medications**

Nerve blocks or trigger point injections in the previous 8 weeks prior to study or at any time during the study are prohibited. Prior exposure to biologics or drugs specifically targeting the CGRP pathway in the 6 months, or 5 half-lives, prior to or during the study are also prohibited.

## 7. Discontinuation of Study Intervention and Participant Discontinuation/Withdrawal

### 7.1. Discontinuation of Study Intervention

In rare instances, it may be necessary for a participant to permanently discontinue (definitive discontinuation) study intervention. If study intervention is definitively discontinued, the participant will not remain in the study. See the SoA for data to be collected at the time of discontinuation of study intervention and for any further evaluations that need to be completed.

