**Data Monitoring Committee: No**

## 1.2. Schedule of Activities (SoA)

Procedure	Screening	Treatment				Early Discontinuation
	Visit 1 Day -33 to Day -28	Visit 2 (Enrollment) Day 1	Visit 3 Day 29 ± 3	Visit 4 Day 57 ± 3	Visit 5 Day 85 ± 3	
Informed consent	X					
Height	X					
Weight	X	X	X	X	X	X
Vital signs	X	X	X	X	X	X
Demography	X					
Physical examination	X	X	X	X	X	X
Neurological examination	X					
Medical history (includes migraine history and substance usage)	X					
Prior and concomitant medications history	X					
Urine pregnancy test (WOCBP only)	X	X	X	X	X	X
Laboratory assessments (CMP)	X				X	X
12-lead ECG	X				X	X

This document, including any source code, is the property of [Clinvest Research LLC](#), and may contain proprietary, confidential, or legally privileged information. No part of this report, or any information contained therein, may be disseminated without the written consent of [Clinvest Research LLC](#).

Procedure	Screening	Treatment				Early Discontinuation
	Visit 1 Day -33 to Day -28	Visit 2 (Enrollment) Day 1	Visit 3 Day 29 ± 3	Visit 4 Day 57 ± 3	Visit 5 Day 85 ± 3	
PHQ-9	X	X	X	X	X	X
Inclusion and exclusion criteria	X	X				
Dispense activity tracker	X					
Dispense diary URL and instructions	X					
Migraine Interictal Burden Scale (MIBS-4)	X	X	X	X	X	X
Neuro-QoL Sleep Disturbance Short Form (SDSF)		X	X	X	X	X
PROMIS-29		X	X	X	X	X
Work Productivity and Activity Impairment-Migraine (WPAI-M)		X	X	X	X	X
General Self-Efficacy Short Form (GSE-SF)		X	X	X	X	X
Brief Measure of Worry Severity (BMWS)		X	X	X	X	X
AE review		X	X	X	X	X
SAE review		X	X	X	X	X
Diary review		X	X	X	X	X
Concomitant medication review		X	X	X	X	X
IP injection		X	X	X		

This document, including any source code, is the property of [Clinvest Research LLC](#), and may contain proprietary, confidential, or legally privileged information. No part of this report, or any information contained therein, may be disseminated without the written consent of [Clinvest Research LLC](#).

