### 7.2. Participant Discontinuation/Withdrawal from the Study

- A participant may withdraw from the study at any time at his/her own request, or may be withdrawn at any time at the discretion of the investigator for safety, behavioral, compliance, or administrative reasons. This is expected to be uncommon.
- At the time of discontinuing from the study, if possible, an early discontinuation visit should be conducted, as shown in the SoA. See SoA for data to be collected at the time of study discontinuation and follow-up and for any further evaluations that need to be completed.
- The participant will be permanently discontinued both from the study intervention and from the study at that time.
- If the participant withdraws consent for disclosure of future information, the sponsor may retain and continue to use any data collected before such a withdrawal of consent.
- If a participant withdraws from the study, he/she may request destruction of any samples taken and not tested, and the investigator must document this in the site study records.

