### 9.2. Sample Size Determination

To determine the needed sample size for this study we utilized G\*Power Version 3.1.9.3 to conduct a power analysis for the Primary Endpoint analysis (repeated measures ANOVA, within-between interaction) comparing baseline MIBS-4 scores to treatment month(s) MIBS-4 scores between 50% responders and non-responders. Based on prior research, we expect an approximate equal proportion of responders and non-responders in this open-label study. The power analysis indicated that a total of 36 subjects would be adequate to detect a medium effect ( $f= 0.25$ ), with alpha set at 0.05, and a power of .95. To account for a 10% early withdrawal rate, a total of 40 subjects should be enrolled in the study.

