### 9.3. Populations for Analyses

The following populations are defined:

Population	Description
Full Analysis Population	All participants enrolled and with at least one administration of IP, will be included in this study population. The Full Analysis Population will be used to analyze the primary efficacy and safety endpoints

Note: Other populations may be defined in the SAP.

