### **Female Participants who become pregnant**

- The investigator will collect pregnancy information on any female participant who becomes pregnant while participating in this study. The initial information will be recorded on the appropriate form and submitted to the sponsor within 24 hours of learning of a participant's pregnancy.
- The participant will be followed to determine the outcome of the pregnancy. The investigator will collect follow-up information on the participant and the neonate and the information will be forwarded to the sponsor. Generally, follow-up will not be required for longer than 6 to 8 weeks beyond the estimated delivery date. Any termination of pregnancy will be reported, regardless of fetal status (presence or absence of anomalies) or indication for the procedure.
- While pregnancy itself is not considered to be an AE or SAE, any pregnancy complication or elective termination of a pregnancy for medical reasons will be reported as an AE or SAE.
- A spontaneous abortion (occurring at <22 weeks gestational age) or still birth (occurring at >22 weeks gestational age) is always considered to be an SAE and will be reported as such.
- Any post-study pregnancy related SAE considered reasonably related to the study intervention by the investigator will be reported to the sponsor as described in Section 8.3.4. While the investigator is not obligated to actively seek this information in former study participants, he or she may learn of an SAE through spontaneous reporting.

Any female participant who becomes pregnant while participating in the study will discontinue study intervention or be withdrawn from the study.

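### Stopping study drug also ends diary and MIBS-4 collection, so later data are missing by rule for participants who must still be analysed and classified as responders or non-responders

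*Combined protocol and SAP*

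**What the plan says.** Section 7.1 introduces discontinuation as uncommon ("In rare instances, it may be necessary for a participant to permanently discontinue") and then ties it to leaving the study: "If study intervention is definitively discontinued, the participant will not remain in the study". Section 7.2, on withdrawal, says the same from the other side: "The participant will be permanently discontinued both from the study intervention and from the study at that time".

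The only measurement planned after that decision is an exit visit: "if possible, an early discontinuation visit should be conducted, as shown in the SoA". The Schedule of Activities (section 1.2) marks MIBS-4, the other questionnaires and diary review in the Early Discontinuation column. It schedules nothing later.

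Section 9.3 defines the population for the primary endpoint without regard to whether dosing continued: "All participants enrolled and with at least one administration of IP, will be included in this study population". Section 9.4.1 allows LOCF for missing data where appropriate. Section 9.2 plans for losses: "To account for a 10% early withdrawal rate, a total of 40 subjects should be enrolled in the study".

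In Appendix 4 (10.4), a participant who becomes pregnant "will discontinue study intervention or be withdrawn from the study", which words the two as alternatives.

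**The concern.** The primary analysis relates MIBS-4 over 12 weeks to migraine-day response. The grouping comes from the electronic diary (8.1.2) and the outcome from an electronic questionnaire (8.1.1). Neither needs an injection to be given, yet section 7.1 cuts off both together.

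Such a participant is still in the analysis set. Response status then rests on a truncated diary. The exit MIBS-4, or the last visit score if no exit visit takes place, may be carried forward to the 4-week time points that were never observed. The protocol defines neither the period over which 50% response is judged nor how an early leaver is classified.

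If participants who stop differ in response from those who continue, the responder versus non-responder difference may be biased. A later SAP can set classification and imputation rules, but it cannot recover data that were not collected.

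**Working it through.** **1. The plan's own figure.** Section 9.2 gives f = 0.25, alpha = 0.05, power 0.95, N = 36 and 40 enrolled. The design gives k = 2 groups, and Visits 2 to 5 give m = 4 measurements. Two inputs are not stated and are assumed: correlation between repeated measures ρ = 0.5 and sphericity ε = 1.

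- λ = f²·N·m/(1 − ρ) = 0.0625 × 36 × 4 / 0.5 = 18
- df1 = (k − 1)(m − 1) = 3; df2 = (N − k)(m − 1) = 34 × 3 = 102
- Power from the noncentral F = 0.952, and 36 is the smallest even N that reaches 0.95
- 36 / 0.9 = 40

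Both figures reproduce. They depend on ρ: at N = 36, power is 0.852 for ρ = 0.3 and 0.998 for ρ = 0.7.

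**2. What one participant loses.** Injections are scheduled at Visits 2, 3 and 4, and post-baseline MIBS-4 at Visits 3, 4 and 5.

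| Stopping point | Scheduled MIBS-4 missed | Exit reading |
|---|---|---|
| After the Visit 2 injection, before Visit 3 | 3 (Visits 3, 4, 5) | One, if the exit visit is held |
| At Visit 3, second injection not given | 2 (Visits 4, 5) | Taken at that attendance |
| After the Visit 3 injection, before Visit 4 | 2 (Visits 4, 5) | One, if the exit visit is held |
| At Visit 4, third injection not given | 1 (Visit 5) | Taken at that attendance |
| After the Visit 4 injection | No injection left to stop | – |

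Three missed scores is the worst case.

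**3. How many participants.** 10% of 40 = 4. Section 9.2 expects roughly equal groups, so about 20 and 20.

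- All 4 non-responders: 4/20 = 20% against 0/20 = 0%
- 3 of 4 non-responders: 3/20 = 15% against 1/20 = 5%
- Even split: 2/20 = 10% in each group

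These are ceilings at the planned rate. The 10% covers all early withdrawals, including people who leave by choice or are lost to follow-up and whom a changed rule could not retain.

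**4. Effect on power.** For unequal groups with the same mean difference, f² is multiplied by 4p(1 − p).

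- All 40 retained (20/20): 0.970
- 4 lost evenly (18/18): 0.952
- 4 lost, all non-responders (20/16): p = 20/36, 4p(1 − p) = 0.988, λ = 17.8, power 0.949

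One-sided loss at the planned rate costs about 0.3 percentage points against balanced loss.

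**5. Possible size of bias (illustration).** Assume normally distributed MIBS-4 changes, 20% of non-responders leaving, and their later data absent and not imputed. With q = 0.2 and correlation r between leaving and poor MIBS-4 change, the mean of the remaining non-responders shifts by r·φ(z_q)/(1 − q) = r × 0.280/0.8 = 0.35r.

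- r = 0.2: 0.07 SD
- r = 0.5: 0.17 SD
- r = 0.8: 0.28 SD
- Exactly the worst 20% leave: 0.35 SD

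The shift makes the remaining non-responders look better and so narrows the group difference. Under LOCF, the bias depends instead on how the carried score compares with the unobserved later scores. The documents do not allow that to be calculated.

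**The case against.** The case for leaving the rule alone has several parts.

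- **Few people are affected.** The protocol calls drug discontinuation rare and withdrawal uncommon. This stands, and it limits both benefit and cost.
- **There is an exit measurement.** MIBS-4 and diary review are scheduled at early discontinuation. This stands, but the visit is conditional, is not tied to a 4-week time point, and does not replace later months.
- **Off-drug scores change the question.** The endpoint compares groups within treated subjects, and the hypothesis in 9.1 refers to three months of dosing. There is no randomised contrast to protect. Participants who stop may also want another preventive, while 5.1 and 6.5 require preventive use to stay unchanged during the study. This stands against putting post-stop scores into the primary analysis without comment. It does not stand against collecting them.
- **The SAP may deal with it.** Section 9.4 defers detail to a SAP that supersedes the protocol. That holds for classification and imputation, but not for data collection.

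Three stronger readings are tempting and are not supported:

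- A reader might infer that the comparison loses one of its two groups. At the planned rate at least 16 of about 20 non-responders complete follow-up, and every dosed participant stays in the analysis set.
- A reader might infer that those who stop are mainly non-responders. The documents do not say so. Section 7.2 gives the participant's own request or safety, behavioural, compliance or administrative grounds, does not list lack of efficacy, and stopping for tolerability does not imply non-response.
- A reader might take the Appendix 4 wording as proof that the plan elsewhere lets participants stay on study off drug. It concerns pregnancy only and is better read as loose drafting that needs reconciling.

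**Conclusion.** The point holds as a data-collection weakness. The protocol makes later diary and MIBS-4 data missing by rule in participants it must still analyse and classify, although both could be collected without an injection.

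The number affected is unknown and is at most 4 of 40 at the planned withdrawal rate. Each could miss one to three scheduled MIBS-4 scores, less any exit reading. The risk is bias in the responder versus non-responder comparison. It arises only if stopping is related to response or to MIBS-4 change, which is plausible but not documented. The illustrative shifts of 0.07 to 0.28 SD assume that all four losses are non-responders and that nothing is imputed, so they indicate scale and do not predict this trial's result. The effect on power is negligible (0.949 against 0.952, assuming ρ = 0.5 and ε = 1).

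The remedy is cheap and available only through the protocol, so the sponsor should act on it. It does not threaten the trial's ability to run its primary analysis.

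**What to change.** - **Amend 7.1** so that a participant who stops study intervention, does not withdraw from the study and is not withdrawn by the investigator under 7.2 is asked to continue the diary and to complete MIBS-4 and the other questionnaires at the remaining scheduled visits, without injection. Keep the early discontinuation visit for those who leave the study.
- **Flag** every post-stop score and any new preventive, and state how the preventive-stability requirement in 5.1 and 6.5 applies to these participants.
- **In the SAP**, report the primary comparison with and without post-stop data, name in advance which is primary, and state how early leavers are classified as responders or non-responders.
- **Reconcile** 7.1, 7.2 and the pregnancy wording in Appendix 4.

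The cost is a protocol amendment, consent wording and at most three already scheduled visits for each participant who stops, so at most 3 × 4 = 12 visits at the planned rate and probably fewer. Some scores will be off drug and need separate handling. No change to when or why treatment is stopped is proposed.
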